#### **11.2.3.3 Duration of platelet response**

Summary statistics will be presented.

#### **11.2.3.4 Summary statistics of platelet count**

The variables to be analyzed are as follows:

- Platelet count
- Change from baseline in platelet count

Summary statistics will be presented. Additionally, medians and quartiles will be presented graphically.

#### **11.2.3.5 Distribution of platelet count**

The variables to be analyzed are as follows:

- Platelet count:  $< 15000$ ,  $15000 \leq < 30000$ ,  $30000 \leq < 50000$ ,  $\geq 50000/\mu\text{L}$
- Change from baseline in platelet count:  $< 20000$ ,  $\geq 20000/\mu\text{L}$

The numbers and percentages of subjects will be presented.

### **11.2.3.6 Individual plots of platelet count**

Individual plots and a swimmer plot will be presented for the change in platelet count in each subject. The dates to be displayed in the figures are as described in “[11.2.1.6 Individual plots of platelet count](#).”

### **11.2.3.7 Summary statistics of quality of life assessment (SF-36)**

Summary statistics will be presented.

## **11.2.4 Evaluation in the non-dosing period**

Applicable period: Non-dosing period

### **11.2.4.1 Summary statistics of platelet count**

The variables to be analyzed are as follows:

- Platelet count
- Change from baseline in platelet count
- Change in platelet count from the start of the non-dosing period

Summary statistics will be presented.

### **11.2.4.2 Distribution of platelet count**

The variables to be analyzed are as follows:

- Platelet count:  $< 15000$ ,  $15000 \leq < 30000$ ,  $30000 \leq < 50000$ ,  $\geq 50000/\mu\text{L}$
- Change from baseline in platelet count:  $< 20000$ ,  $\geq 20000/\mu\text{L}$

The numbers and percentages of subjects will be presented.

### **11.2.4.3 Individual plots of platelet count**

Individual plots will be presented for the change in platelet count in each subject.

The number of days will be shown on the horizontal axis. The platelet count in unscheduled measurements and after the use of rescue medication will also be displayed.

### **11.2.4.4 Decrease in platelet count after dose interruption**

The variables to be analyzed are as follows:

- Platelet count of  $< 10000/\mu\text{L}$  with a decrease from baseline of  $\geq 10000/\mu\text{L}$

The number and percentage of subjects who met the conditions of the analysis variables during the non-dosing period will be presented.

### **11.2.4.5 Summary statistics of quality of life assessment (SF-36)**

Summary statistics will be presented.

## **11.2.5 Evaluation in Period III**

Applicable period: Period III

### **11.2.5.1 Summary statistics of platelet count**

The variables to be analyzed are as follows:

- Platelet count
- Change from baseline in platelet count

Summary statistics will be presented.

### **11.2.5.2 Distribution of platelet count**

The variables to be analyzed are as follows:

- Platelet count:  $< 15000$ ,  $15000 \leq < 30000$ ,  $30000 \leq < 50000$ ,  $\geq 50000/\mu\text{L}$
- Change from baseline in platelet count:  $< 20000$ ,  $\geq 20000/\mu\text{L}$

The numbers and percentages of subjects will be presented.

### **11.2.5.3 Individual plots of platelet count**

Individual plots will be presented for the change in platelet count in each subject.

## **11.2.6 Evaluation in R788 treatment period**

Applicable period: R788 treatment period

### **11.2.6.1 Platelet response rate**

The variables to be analyzed are as follows:

- Platelet count:  $\geq 50000/\mu\text{L}$

The number and percentage of subjects achieving a platelet count of  $\geq 50000/\mu\text{L}$  at least one analysis visit between the day of first administration of R788 and Week 52 of Period II will be presented.

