## 3. Analysis Group

Unless otherwise specified, the analysis will be performed on the following subjects and data. For FAS analysis, “treated subjects” will be handled as “randomized subjects.”

- 1) Evaluation in Period I
  - R788 group: Period I data of subjects who received R788 in Period I
  - Placebo group: Period I data of subjects who received placebo in Period I
- 2) Evaluation during long-term treatment of R788
  - R788 group: The analysis will be performed on the following subjects and data:
    - Period I data of subjects who received R788 in Period I
    - Period II data of subjects who received R788 in Period I, completed treatment with R788 in Period I and transitioned to Period II (subjects on long-term treatment of R788)

3) Evaluation in Period II

- R788-R788 group: Period II data of subjects who received R788 in Period I and early transitioned to Period II after discontinuing Period I
- P-R788 group: Period II data of subjects who received placebo in Period I and transitioned to Period II

4) Evaluation in non-dosing period

- R788 group: Non-dosing period data of subjects who transitioned to the non-dosing period (subjects who transitioned from Period II to Period III without non-dosing period are excluded).

5) Evaluation in Period III

- R788 group: Period III data of subjects who transitioned to Period III

6) Evaluation in R788 treatment period

- R788 group: The analysis will be performed on the following subjects and data:
  - Data from Period I, Period II, and Period III of subjects who received R788 in Period I
  - Data from Period II and Period III of subjects who received placebo in Period I and transitioned to Period II

7) Evaluation in the entire study period

- R788-R788 group: Data from Period I, Period II, non-dosing period, and Period III of subjects who received R788 in Period I
- P-R788 group: Data from Period I, Period II, non-dosing period, and Period III of subjects who received placebo in Period I

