## 2) Evaluation during long-term treatment of R788

**CONFIDENTIAL**

Kissei Pharmaceutical Co., Ltd.

Protocol No.: R788-1301

Statistical Analysis Plan

Version: 3.0

**Table 5.9-3** Analysis visits during long-term treatment of R788

Variables evaluated	Analysis visit
Platelets	Screening A, B, Day 1, Week 2 to 24 (every 2 weeks), Week 28 to 52 (every 4 weeks)
Treatment dose	Day 1, Week 2 to 24 (every 2 weeks), Week 28 to 52 (every 4 weeks)
QOL assessment (SF-36)	Day 1, Week 4, 12, 24, 52
ITP Bleeding Score	Screening A, Day 1, Week 2 to 24 (every 2 weeks), Week 28 to 52 (every 4 weeks), LOV
ECOG Performance Status	Screening A, Day 1, Week 4 to 52 (every 4 weeks), LOV
Hematology (excluding platelets)	Screening A, B, Day 1, Week 2 to 24 (every 2 weeks), Week 28 to 52 (every 4 weeks), LOV
Serum chemistry	Screening A, Day 1, Week 2 to 24 (every 2 weeks), Week 28 to 52 (every 4 weeks), LOV
Urinalysis	Screening A, Day 1, Week 4 to 24 (every 4 weeks), Week 28 to 52 (every 12 weeks), LOV
Immunoglobulin test	Screening A, Day 1, Week 24, Week 52, LOV
Vital signs	Screening A, B, Day 1, Week 2 to 24 (every 2 weeks), Week 28 to 52 (every 4 weeks), LOV

**Table 5.9-4** Time Windows for Each Analysis Visit during Long-term Treatment of R788

Analysis visit	Target study day a)	Lower limit	Upper limit
Screening A	-28	-31	-25
Screening B	-14	-17	-11
Day 1	1	1	1
Week 2 to 24	$7 \times x + 1^b)$	Target study day -3	Target study day +3
Week 28 to 52	$7 \times x + 1^b)$	Target study day -7	Target study day +7

a) The first day of study drug administration in Period I is defined as Day 1, and the day before the first day of study drug administration as Day -1.

b) x: Number of weeks

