### 3) Evaluation in Period II

The following data will be used as Week 24 to 52 data:

- Data from Week 24 to 52 of subjects who received placebo in Period I, completed Period I, and transitioned to Period II.
- Data from early transition Day 1 to early transition Week 28 of subjects who discontinued Period I and early transitioned to Period II.

**Table 5.9-5** Analysis Visits in Period II

Variables evaluated	Analysis visit
Platelets	Week 24 to 52 (every 4 weeks)
Treatment dose	Week 24 to 52 (every 4 weeks)
QOL assessment (SF-36)	Week 24, Week 52
ITP Bleeding Score	Week 24 to 52 (every 4 weeks), LOV
ECOG Performance Status	Week 24 to 52 (every 4 weeks), LOV
Hematology (excluding platelets)	Week 24 to 52 (every 4 weeks), LOV
Serum chemistry	Week 24 to 52 (every 4 weeks), LOV
Urinalysis	Week 24, Week 28 to 52 (every 12 weeks), LOV
Immunoglobulin test	Week 24, Week 52, LOV
Vital signs	Week 24 to 52 (every 4 weeks), LOV

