## 6) Evaluation in R788 treatment period

Day 1 of the R788 treatment period is defined as the first day of study drug administration in Period I for subjects who received R788 in Period I, and as the first day of study drug administration in Period II for those who received placebo in Period I and transitioned to Period II. No analysis visit-specific analysis will be performed for evaluation in the R788 treatment period.

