## 11.3 Subgroup Analysis of Efficacy

- 1) The analyses described in “[11.2.6.1 Platelet response rate](#)” will be performed for each line of therapy (2nd line, 3rd line or later).
- 2) At the first data cut-off, the analyses described in “[11.2.2.1 Achievement rates for platelet count-related endpoints](#)” will be performed, excluding subjects who are still in Period II.
- 3) Summary statistic of platelet count in “[11.2.1.4 Summary statistics of platelet count](#)” will be presented for responders and non-responders in stable platelet response. Additionally, medians and quartiles will be presented graphically for responders and non-responders in the R788 group, and for the placebo group.
- 4) For the data in Period I, the median platelet count after the administration of the investigational product will be calculated for each subject, and the summary statistics will be presented for the R788 group, for responders and non-responders in stable platelet response in the R788 group, and for the placebo group.

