## 16. Changes from the Protocol

### 16.1 Changes in Statistical Analysis Plan Version 1.0

- 1) In “[3 Analysis Group](#),” the “period I data of subjects who discontinued R788 treatment in Period I” were added to the evaluation during long-term treatment of R788.

Reason: The purpose of this analysis was to evaluate the efficacy and safety of R788 from the start to the end of treatment with the product. Therefore, it was considered appropriate to include subjects who discontinued Period I in the analysis.

- 2) In “[3 Analysis Group](#),” evaluation in the entire study period was added.

Reason: To evaluate platelet response throughout the entire period after study entry.

- 3) In “[5.9 Analysis Visits](#),” the baseline for change calculation was defined as Day 1 of Period I for all periods.

Reason: In the protocol, the baseline was defined as Day 1 of each period. However, it was considered appropriate to use the value not affected by study drug administration as the baseline value.

- 4) In “[6.3.1 Timing of analysis](#),” the scope of data to be cutoff was changed, and variables to be analyzed were clarified.

Reason: To include Period II data in the first data cutoff and the non-dosing period data in the second data cutoff. In addition, variables to be analyzed at the time of cutoff were clarified.

- 5) Evaluation of line of therapy-related variables was added to “[9.1 Subject Demographics](#),” and evaluation of achievement rate of platelet-related endpoints was added to “[11.2.6.1 Platelet response rate](#)” and “[11.3 Subgroup Analysis of Efficacy](#).”

Reason: To evaluate the effect of line of therapy on efficacy, as evaluated in the paper of foreign studies.

- 6) In “[7 Definition of Derived Data](#),” the definition of the start day of platelet response was changed to “the first day after the start of study treatment in each period on which a platelet count of  $\geq 50000/\mu\text{L}$  for at least 28 consecutive days without the use of rescue medications was achieved.”

Reason: To evaluate stable maintenance of platelet count.

- 7) In “[11.1 Primary Endpoint](#),” sensitivity analysis of the primary endpoint planned in the protocol was deleted.

Reason: A blind review confirmed that no subject would need imputation of missing

platelet count data for the evaluation of stable platelet response. It was thus decided not to perform sensitivity analysis because no imputation would be performed.

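### The any-visit platelet response rate in SAP 11.2.6.1 pools subjects with up to 19 and up to 7 post-dose R788 visits, so its line-of-therapy breakdown depends modestly on arm mix

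*SAP*

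**What the plan says.** SAP 11.2.6.1 asks for the number and percentage of subjects with a platelet count of at least 50000/µL at "at least one analysis visit between the day of first administration of R788 and Week 52 of Period II".

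SAP 3, item 6 defines the group for the R788 treatment period from two sources:
- The R788 arm, which contributes everything from its first dose in Period I onward.
- The placebo arm, which contributes only once it is on R788: "Data from Period II and Period III of subjects who received placebo in Period I and transitioned to Period II"

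For the second source, SAP 5.9, item 6 sets Day 1 "as the first day of study drug administration in Period II for those who received placebo in Period I and transitioned to Period II". That item has no visit table of its own, so the platelet visits have to be read from the neighbouring tables:
- Table 5.9-3 (long-term R788): "Screening A, B, Day 1, Week 2 to 24 (every 2 weeks), Week 28 to 52 (every 4 weeks"
- Table 5.9-5 (Period II): "Week 24 to 52 (every 4 weeks"

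SAP 11.3 1) says that the 11.2.6.1 analysis "will be performed for each line of therapy (2nd line, 3rd line or later"). SAP 16.1, item 5 gives the reason: "To evaluate the effect of line of therapy on efficacy, as evaluated in the paper of foreign studies".

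Three further provisions bear on the point. Protocol 8.8.4.4 names platelet count as the only stratification factor. SAP 6.1 rules out covariate adjustment. SAP 11.2.6.2, the next output, is to be shown for the pooled group and for the R788-R788 and P-R788 groups, but 11.2.6.1 and 11.3 1) state no such split.

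**The concern.** An at-least-one-visit response becomes more likely as more visits are examined and as exposure lengthens. The two sources of the pooled group differ in both respects by design. The pooled rate is therefore a weighted average of two differently defined quantities, and the weights are the arm proportions.

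That matters little for the overall rate if it is read as ever having responded on R788. It matters more in 11.3 1), where the rate is set side by side for two line-of-therapy subgroups in order to look at the effect of line. The arm mix within each subgroup is left to chance. If it differs, part of the difference between lines reflects how long and how often subjects were observed.

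**Working it through.** **1. Visit counts.** Every 2 weeks from Week 2 to Week 24 gives 12 visits, which reproduces the 12 stated in SAP 11.2.1.2. Every 4 weeks from Week 28 to Week 52 gives 7.
- R788 arm, both periods completed: 12 + 7 = 19 post-dose visits over 52 weeks.
- R788 arm, early transition: the last Period I visit falls between Week 12 (6 visits) and Week 22 (11 visits), so 6 + 7 = 13 to 11 + 7 = 18.
- Placebo switchers: 7 visits over 28 weeks.

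These are maxima. Subjects who withdraw have fewer.

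**2. A boundary ambiguity.** The window opens on the day of the first R788 dose. For the R788 arm, the Day 1 count cannot be a response, because inclusion criterion 4 caps each qualifying count at 35000/µL. For placebo completers, Week 24 is a listed Period II visit, yet Protocol 8.6.1 starts the Period II drug after that visit. Read literally, a pre-R788 count could be scored as an R788 response.

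**3. Effect on the rate.** The documents give neither a per-visit response probability p nor a within-subject correlation ρ, so both are assumed. The drug effect is taken as equal in both arms.
- Independent visits: P(n) = 1 − (1 − p)^n.
- Correlated visits (beta-binomial): P(n) = 1 − ∏ (b + i)/(a + b + i) for i = 0 to n − 1, with a = p(1/ρ − 1) and b = (1 − p)(1/ρ − 1).

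The value p = 0.178 is borrowed from the planning rate in Protocol 8.9.2. That is a rate of stable response, not a per-visit rate, so it serves only as an illustration.

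If the two line subgroups differ in placebo share by d, and line itself has no effect, their rates differ by d × [P(19) − P(7)]. A 2:1 mix against a 1:2 mix means d = 1/3.

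| p | ρ | P(19) | P(7) | Gap (points) | Line difference at d = 1/3 (points) |
|---|---|---|---|---|---|
| 0.178 | 0 | 97.6% | 74.6% | 22.9 | 7.6 |
| 0.178 | 0.3 | 65.0% | 49.8% | 15.3 | 5.1 |
| 0.178 | 0.5 | 48.3% | 38.6% | 9.7 | 3.2 |
| 0.178 | 0.7 | 34.7% | 29.4% | 5.2 | 1.7 |
| 0.178 | 0.9 | 23.1% | 21.5% | 1.6 | 0.5 |
| 0.10 | 0.3 | 43.9% | 31.4% | 12.5 | 4.2 |
| 0.10 | 0.5 | 30.5% | 23.5% | 7.0 | 2.3 |

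Gaps and differences are taken before rounding. At p = 0.178 and ρ = 0.3 the two mixes give 59.9% and 54.8%. Early-transition R788 subjects narrow the gap: with 13 visits the rate is 59.6%, against 65.0% with 19.

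**4. How likely such a mix is.** Protocol 8.9.1 plans 16 and 8 subjects. Because the whole sample is 2:1, a realistic case with d = 1/3 is a 12/12 split by line with 6 placebo subjects in one subgroup and 2 in the other (50.0% − 16.7% = 33.3 points). The rates at p = 0.178 and ρ = 0.3 are then 57.4% and 62.5%, again 5.1 points apart. If allocation is unrelated to line and all subjects enter the group, the hypergeometric probability of a placebo-share difference of at least 25 points is 0.19 for a 12/12 split and 0.36 for an 8/16 split.

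**5. First data cutoff.** SAP 6.3.1 then takes Period II data only from Period II completers. SAP 11.3 2) removes ongoing subjects for 11.2.2.1 but not for 11.2.6.1, so the difference in observed visits may be wider at that cutoff.

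**The case against.** The strongest reply is that nothing inferential rests on this output. SAP 11.2.6.1 asks for a count and a percentage, and 11.3 1) adds no test, confidence interval or between-line difference. SAP 6.5 calls all non-primary variables reference only. With an assumed 12 subjects per line and 6 responders, the Clopper-Pearson interval runs from about 21% to 79%, so a line effect could hardly be read from it in any case. All of this stands and sets the priority.

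A reader might go further and infer that the line comparison could be badly distorted. With independent visits and an isolated-count probability of 2% or 5% per visit, 1 − (1 − p)^n gives 32% v 13%, or 62% v 30%, for 19 v 7 visits. The arithmetic is right, but the documents do not support that inference. These are contrasts between arms, and they carry over to the line subgroups only if arm and line coincide completely. Independence is also implausible for repeated platelet counts in one subject. In addition, SAP 5.5.1 sets counts within 28 days after rescue to missing, which removes one source of isolated high values.

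Ever having responded on R788 by Week 52 is also a legitimate descriptive quantity. The stated reason refers to a paper on the foreign studies, which is not available here, so replacing the definition outright could damage the intended comparison. Arm-specific results appear elsewhere (SAP 11.2.1.1, 11.2.2.1, 11.2.3.2 and the individual plots), but none of them is broken down by line. The objection limits the weight of the point; it does not remove the dependence on arm mix.

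**Conclusion.** The point holds as a minor one. The unequal number of visits and length of exposure are built into 11.2.6.1. Allocation, adjustment and presentation do not protect the breakdown in 11.3 1) from arm mix. The direction is predictable if the drug effect is the same in both arms: more R788-arm subjects tends to mean a higher rate.

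The size is not in the documents. At p = 0.178 and ρ = 0.3 it is about 5 points for a one-third difference in placebo share. It falls to about 3 points at ρ = 0.5 and below 1 point at ρ = 0.9. At a given correlation it grows only as arm and line become more strongly confounded. The primary endpoint and its test are untouched.

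**What to change.** In SAP 11.2.6.1 and 11.3 1), do one or both of the following:
- Present the rate separately for the R788-R788 and P-R788 groups, as 11.2.6.2 already does.
- Present it over a common window, namely the first 28 weeks after the first R788 dose at about 4-weekly visits. This gives 7 visits in each arm: Weeks 4 to 28 for the R788 arm and Weeks 28 to 52 for placebo switchers. Early-transition R788 subjects restart their visit schedule at ET Day 1 and do not fall on this grid, so state a nearest-visit rule for them.

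In either case, state that the placebo arm's pre-R788 Week 24 count is not eligible as a response. Keep the pooled rate up to Week 52 alongside for comparison with the foreign studies.

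The cost is SAP wording and some extra table columns, since the data are already collected. The split by arm leaves small denominators, at most 16 and 8 before dividing by line. The common window drops 12 of the R788 arm's 19 visits, so that arm's rate will be somewhat lower.

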8.6 Dose and Administration

8.6.1 Dose and administration

Dose and administration method are shown in Figure 8.6.1-1 and Figure 8.6.1-2.

1) Screening period

No study drug is administered.

2) Period I

R788 or matching placebo is administered orally for 24 weeks. On Day 1, 100 mg of the study drug will be administered at the study institution. This must be the only administration of the study drug on Day 1, irrespective of the time of administration. The study drug will be administered twice daily beginning on the next day and the dose will be adjusted according to "8.6.2 Dose adjustment" during Period I. Morning and evening doses should be at least 8 hours apart and should be taken at approximately the same time each day, with or without food during Period I. In principle, subjects will visit the study institution in the morning without taking the study drug and take the study drug at the study institution in the morning to measure drug concentration at Weeks 2 and 6. In principle, subjects will take the study drug at 1 to 4 hours before visiting the study institution in the morning at Week 4 and Weeks 8 to 24.

3) Period II

R788 is orally administered for 28 weeks.

(1) Subjects who completed Period I

The study drug for Period I is continued until the visit at Week 24 and the study drug for Period II is initiated after the visit at Week 24 (if study drug in Period II is initiated as twice daily, subjects who took the study drug for Period I in the morning on the day of the visit start the study drug for Period II from the evening of the same day). The dose and administration at the start of the study drug for Period II is as follows.

- If platelet count at Week 24 is $\geq 50000/\mu$ L, study drug in Period II is initiated with the last dose and administration in Period I.
- If platelet count at Week 24 is $< 50000/\mu$ L and last dose and administration in Period I is 150 mg *bid*, study drug in Period II is initiated with 100 mg *bid*.
- If platelet count at Week 24 is $< 50000/\mu$ L and last dose and administration in Period I is 100 mg qd, 150 mg qd, or 100 mg bid, study drug in Period II is initiated with the last dose and administration in Period I.

(2) Early transition subjects

The study drug for Period II is initiated after the visit on ET Day 1 (if study drug in Period II is initiated as twice daily, subjects who took the study drug for Period I in the

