14.6.4 Vital signs

- 1) For vital signs (systolic blood pressure, diastolic blood pressure, pulse rate, and body temperature), the summary statistics of measured values and changes from the baseline will be presented. Scatter plot of measured values before and after administration will be presented.
- 2) The maximum systolic blood pressure after the dosing of the study treatment in each period will be categorized into < 140 mmHg, \geq 140 mmHg to < 160 mmHg, \geq 160 mmHg to < 180 mmHg, and \geq 180 mmHg and frequency distribution will be shown.
- 3) The maximum diastolic blood pressure after the dosing of the study treatment in each period will be categorized into $< 90 \text{ mmHg}, \ge 90 \text{ mmHg}$ to $< 100 \text{ mmHg}, \ge 100 \text{ mmHg}$ to < 110 mmHg, and $\ge 110 \text{ mmHg}$, and frequency distribution will be shown.
- 4) For systolic and diastolic blood pressure, frequency distribution of the number of times of systolic blood pressure ≥ 140 mmHg or diastolic blood pressure ≥ 90 mmHg after the dosing of the study treatment in each period will be shown. The number of times of systolic blood pressure ≥ 160 mmHg or diastolic blood pressure ≥ 100 mmHg will also be presented in the same manner.

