## 5.9 Analysis Visits

Unless otherwise specified, each analysis variable will be evaluated at the following time points.

- Data obtained outside the time window of analysis visits and data from unscheduled visits

will be excluded from summarization at each time point.

- For analyses of each treatment period, test data obtained outside the range of “the day of the last dose plus the specified number of days” will be excluded from the analysis. The specified number of days is 3 days for Period I and 7 days for Periods II and III.
- The last observed visit (LOV) other than the non-dosing period is defined as the last scheduled visit or the discontinuation visit, whichever is later, performed within the range of “the day of the last dose plus the specified number of days” for each period. The specified number of days is 3 days for Period I and 7 days for Periods II and III.
- The LOV in the non-dosing period is defined as the data for the latest test among all tests performed up to the last day of the non-dosing period.
- For all variables, Day 1 of Period I will be used as a baseline and only changes at time points after Day 1 of each period will be evaluated.
- In the non-dosing period, change from the start of the non-dosing period will be evaluated in addition to the change from Period I Day 1. Time points after Day 1 of the non-dosing period will be evaluated.

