### **12.5.4 Distribution of post-baseline extrema of blood pressure**

The variables to be analyzed are as follows:

- Systolic and diastolic blood pressure: Systolic blood pressure  $\geq 140$  mmHg or diastolic blood pressure  $\geq 90$  mmHg
- Systolic and diastolic blood pressure: Systolic blood pressure  $\geq 160$  mmHg or diastolic blood pressure  $\geq 100$  mmHg

The number and percentage of subjects will be presented for the number of post-baseline scheduled visits with blood pressure values within the above ranges.

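### The R788 response window in SAP 11.2.6.1 can include the pre-dose Week 24 visit of placebo completers, so a platelet count reached on placebo can score as an R788 response

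*SAP*

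**What the plan says.** **Response rate.** SAP 11.2.6.1 (evaluation in the R788 treatment period) counts subjects with 50000/µL or more at "at least one analysis visit between the day of first administration of R788 and Week 52 of Period II". SAP 5.9, item 6, sets Day 1 of that period for switchers "as the first day of study drug administration in Period II for those who received placebo in Period I and transitioned to Period II". SAP 3, item 6, takes their data from Periods II and III.

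Protocol 8.6.1 says that for completers "the study drug for Period II is initiated after the visit at Week 24". Subjects starting twice-daily drug who took their Period I dose that morning "start the study drug for Period II from the evening of the same day".

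SAP 5.9, item 3, lists among the Period II data "Data from Week 24 to 52 of subjects who received placebo in Period I, completed Period I, and transitioned to Period II", and Table 5.9-5 makes Week 24 a Period II platelet visit. SAP 11.3, item 1, repeats the response analysis by line of therapy.

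**Safety extremes.** SAP 5.9 states: "For all variables, Day 1 of Period I will be used as a baseline". SAP 12.4.5 (laboratory extremes) and 12.5.3 (blood pressure maxima) use post-baseline values, and 12.5.4 tabulates "the number of post-baseline scheduled visits" with raised blood pressure. Protocol 14.6.4 limits the blood pressure summaries to values "after the dosing of the study treatment in each period". Protocol 14.6.5 limits the ALT/AST maximum to values after treatment starts in each period.

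**The concern.** The response rate in 11.2.6.1 is meant to describe what happens on R788. A placebo completer's Week 24 count reflects 24 weeks of placebo and no R788. If it lies inside the window, one high count on placebo is enough to make that subject an R788 responder, whatever happens afterwards.

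The error can only favour R788. Subjects randomised to R788 also have a pre-dose visit on their first dosing day, but inclusion criterion 4 caps each eligibility count at 35000/µL, so that visit cannot score. Placebo switchers have no such cap at Week 24.

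The pooled rate and the line-of-therapy subgroups are at stake. One subject weighs more in a subgroup than in the pooled set. A related wording difference could bring the same pre-R788 visit into the Period II safety extremes of the group that switched from placebo.

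**Working it through.** The plan gives no figure for this analysis. Its one design figure, the 89% in Protocol 8.9.2, concerns the primary endpoint. Exact enumeration with 16 and 8 subjects at 17.8% and 2.0% gives 0.893 for a higher R788 estimate, which matches, and nothing here changes it.

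**1. Is the Week 24 visit in the window?**
- Lower bound: the calendar day of first R788 dosing, with no post-dose condition (SAP 11.2.6.1).
- Order at Week 24: visit first, then first Period II dose (Protocol 8.6.1).
- Same day? Yes for a twice-daily start after a morning dose. This is the usual case, because Protocol 9, item 4, asks subjects to take the morning dose before the Week 24 sample. A once-daily subject doses in the morning (Protocol 8.6.2.2) and so may start R788 the next day, which puts the visit just outside.
- Is it an analysis visit? Week 24 is targeted at day 7 × 24 + 1 = 169 and is listed under Period II.
- Is it removed elsewhere? The rule in SAP 5.9 about time points after Day 1 of each period covers changes. Being at or above 50000/µL is a level.

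So the pre-dose count qualifies whenever R788 starts on the visit day.

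**2. Who is exposed?** Placebo completers. Early-transition subjects enter on a platelet criterion (Protocol 8.3.1): below 50000/µL, or a rise of less than 20000/µL from below 15000/µL, hence below 35000/µL. Their ET Day 1 count should rarely qualify.

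**3. Size per subject.** The rate moves only if the subject has no count of 50000/µL or more at any later visit, Weeks 28 to 52. Each such subject adds 1/24 = 4.2 points if all 24 are analysed, or 1/20 = 5.0 points if only 4 of the 8 placebo subjects enter Period II (16 + 4 = 20).

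**4. How likely is a candidate?** Let p be the chance that a placebo completer has a Week 24 count of 50000/µL or more. The documents do not give it. I assume 2% (the placebo stable-response rate in Protocol 8.9.2) to 15%; the upper end is purely an assumption. With 8 completers:

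| p | At least one candidate, 1 − (1 − p)^8 | Expected candidates, 8p | Maximum expected bias, 8p/24 |
|---|---|---|---|
| 2% | 14.9% | 0.16 | 0.7 points |
| 5% | 33.7% | 0.40 | 1.7 points |
| 10% | 57.0% | 0.80 | 3.3 points |
| 15% | 72.8% | 1.20 | 5.0 points |

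The last column assumes that no candidate reaches 50000/µL again on R788. If half do, it halves. With 4 completers, 1 − (1 − p)^4 runs from 8% to 48%.

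**5. Safety extremes.** With baseline at Day 1 of Period I, Week 24 is literally post-baseline, and Period II lists Week 24 chemistry, hematology and vital signs. It is one of (52 − 24)/4 + 1 = 8 scheduled visits. With at most 8 subjects in the placebo-to-R788 group, one misplaced subject moves a row by at least 1/8 = 12.5 points. SAP section 16 records the new baseline and categories, but not a change from the protocol's after-dosing restriction.

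**The case against.** **The window is not fully defined.** SAP 5.9, item 6, gives no visit table for the R788 treatment period and says that no visit-specific analysis is done for it, so a programmer could already leave out the pre-dose visit. That is true, but 11.2.6.1 still relies on analysis visits, and SAP 3 points to Period II data for switchers. The text does not require the exclusion. Elsewhere the SAP states it: duration of response, adverse events in the R788 treatment period and the post-dose bleeding mean are all tied to the time after dosing.

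**The consequence is limited and visible.** This stands. The analysis has no test or group comparison, and SAP 6.5 treats all non-primary variables as reference only. A placebo count of 50000/µL or more at Week 24 also appears in the placebo achievement rate (11.2.1.1) and the individual plots (11.2.7.1). The sustained-response comparison and the Period II rates at Weeks 36, 48 and 52 are not affected.

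**The safety part is a wording conflict.** This also largely stands. The SAP says that it details Protocol section 14, and its section 16.1, item 3, describes the new baseline as one for calculating changes. The after-dosing restriction may still be intended.

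A reader might infer that the reported rate has a 15% to 73% chance of being inflated. It does not: those figures are the chance of a candidate among 8 assumed completers, before asking whether that subject responds later on R788. A reader might also infer that the SAP contradicts the protocol on neutrophils. Protocol 14.6.5 restricts only ALT/AST; the neutrophil, ALP and bilirubin extremes were added in the SAP, and the protocol sets no rule for them.

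**Conclusion.** The response point holds on the text. For a placebo completer who starts R788 on the day of the Week 24 visit, 11.2.6.1 admits a count taken before any R788. Each subject who qualifies on that visit alone raises the pooled rate by about 4.2 points. The chance of such a false responder is at most 15% to 73%, on the assumptions of a 2% to 15% Week 24 placebo rate and 8 completers, and it is lower if candidates respond again on R788 or fewer subjects complete. The case is plausible: Protocol 1.3.2.2 reports that one of 44 placebo subjects entering the overseas extension had already responded on placebo.

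The documents do not support any effect on the primary endpoint or on the randomised comparison. The safety point is secondary. It is an unlogged difference between SAP and protocol on ALT/AST and blood pressure, which matters only if the SAP is programmed literally.

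**What to change.** In SAP 11.2.6.1, count only analysis visits after the first administration of R788, up to Week 52. State that for placebo switchers the first eligible visit is Week 28 or ET Week 4. The line-of-therapy analysis in 11.3 then follows.

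For the Period II evaluation in 12.4.5, 12.5.3 and 12.5.4, restore the protocol's restriction to values after dosing or start of treatment in that period for ALT/AST and blood pressure. Apply the same rule to the neutrophil, ALP and bilirubin extremes, so that all of these summaries use one window.

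The cost is a few words in the SAP and one date condition in the programs. The downside for the sponsor is that the pooled response rate may come out slightly less favourable.
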